### 2.1 Efficacy

Efficacy endpoints are described below. The primary comparisons in this trial will be within a treatment group on the mean change from baseline. The primary comparisons for proportion of subjects achieving a specified endpoint will be between treatment groups.

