## 3. Study Design and Procedures

### 3.1 General Study Design and Plan

This is an 8-week, randomized, open-label, multicenter, efficacy and safety study in subjects with FCD.

The study will be conducted at approximately 20 sites in the USA. Two different dosing regimens (QD and BID) of netarsudil will be investigated for their efficacy in reducing or resolving corneal edema in subjects with FCD. Subjects randomized to the netarsudil QD dosing regimen will be instructed to instill one drop of the Study Artificial Tear in their study eye every morning, and one drop of netarsudil in their study eye

every evening. Subjects randomized to the netarsudil BID dosing regimen will instill one drop of netarsudil in their study eye every morning and evening.

CCT will be measured by ultrasound pachymetry at approximately the same time of day  $\pm$  60 minutes and always before noon (local time), at each of the 5 scheduled visits (Screening, Baseline [Day 1], Week 2, Week 4, and Week 8/Exit). In order to be eligible to participate in the study, subjects will have been diagnosed with visually significant central corneal edema due to FCD, in at least one eye, for no longer than 12 months' duration.

At the Screening visit, the subject's diagnosis of FCD will be confirmed and CCT measured using an ultrasonic pachymeter. IOP and BCVA will also be collected.

At the Baseline visit (Day 1), the eligibility assessments conducted during Screening will be repeated to ensure that the subject meets all criteria for enrollment in the study. The same eye must qualify at both the Screening and Baseline visits. If qualified, the subject will be provided with the V-FUCHS patient reported visual disability questionnaire (Wacker 2018). The subject will be randomized (1:1) into the study and provided with study medication. The subject will also be trained on appropriate techniques for applying eye drops.

At the Week 2 and Week 4 visits, the subject will return to the study site for efficacy and safety assessments.

At the Week 4 visit, any subject randomized to netarsudil QD who, in the opinion of the Investigator, has not responded adequately to treatment, may have their netarsudil dosing frequency increased to BID for the remainder of the study. For these subjects, the morning administration of Study Artificial Tear will be terminated.

At the Week 8 visit, a final assessment of efficacy and safety parameters will be conducted, and the subject will exit the study.

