### 8.4 Data Analysis Conventions

All data analysis will be performed by SDC. Statistical programming and analyses will be performed using SAS® Version 9.4 or higher. Output will be provided in rich text format (RTF) for tables and portable document format (PDF) for tables, and listings using landscape orientation. Unless otherwise specified, all study data for randomized subjects will be listed by treatment group, subject number, visit, and parameter as applicable. Only a disposition listing will be created for screen failure subjects. Summaries will be presented by treatment group and visit as applicable.

Continuous study assessments will be summarized by treatment group and visit as applicable using descriptive statistics (n, mean, median, SD, minimum, and maximum). Minima and maxima will be reported with the same precision as the raw values; means and medians will be presented to one additional decimal place than reported in the raw values. Standard deviations will be presented to two additional decimal places than reported in the raw values. Categorical study assessments will be summarized by treatment group and visit as applicable using discrete descriptive statistics (frequency counts and percentages). All percentages will be rounded to one decimal place (ie, XX.X%). Change from baseline will be calculated as follow-up visit – baseline visit.

Hypothesis testing, unless otherwise indicated, will be performed at a 2-sided with a significant level of 0.10 ( $\alpha = 0.1$ ). Where applicable, 2-sided 90% and 95% confidence intervals (CIs) will be reported. All p-values will be displayed to four decimal places, with p-values less than 0.0001 presented as "<0.0001" and p-values greater than 0.9999 presented as ">0.9999". All odds ratios less than 0.01 will be presented as "<0.01" and all odds ratio greater than 999.99 will be presented as ">999.99". Difference between netarsudil QD and netarsudil BID will be calculated as netarsudil QD – netarsudil BID.

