### 12.3 Secondary Efficacy Analyses

The secondary efficacy analyses will be conducted on the mITT population ODO. Descriptive statistics will be presented by treatment group for both study eye and qualified fellow eye. Summarization and analysis of the mean change from baseline in BCVA at Weeks 4 and 8 and mean change from baseline in mean CCT by ultrasound pachymetry at Week 8 will be completed using a similar strategy as for the primary endpoints described in Section 12.2.

Testing of the proportion of subjects who gained  $\geq 15$  letters (3 lines) in BCVA at Weeks 4 and 8 (separately) and testing of the proportion of subjects with complete resolution of corneal edema at Weeks 4 and 8 (separately), will be completed using logistic regression with fixed effects of treatment and corresponding baseline measure. The adjusted odds ratios, marginal proportion of each treatment group, and difference in marginal proportions along with corresponding two-sided 95% CIs and p-values will be presented. When none of the subjects in both treatment groups achieve a gain of 3 lines in BCVA, no inferential statistics for the testing of the proportions will be produced. Treatment comparisons will also be made using Pearson's chi-squared test or Fisher's exact test if any of the cell counts are less than five as a sensitivity analysis.

Example SAS® code for analyzing categorical outcomes ("Y" when desired criterion is met, "N" if not)

Logistic regression for modeling the treatments effect on outcome:

```
proc logistic data = indata descending alpha = 0.05;
  class treatment (ref = 'BID') / param=glm;
  model outcome = treatment baseline_BCVA;
  lsmeans treatment / diff oddsratio cl exp;
  ods output ParameterEstimates = pe;
run;
```

In the logistic model for the probability of outcome = Y, the following call to "Margins" (a SAS macro) estimates the treatment predictive margins and their difference (the margin effect) and reverses the direction of the difference (QD – BID rather than default BID – QD):

```
%Margins(data = indata,
  class = treatment,
  response = outcome,
  roptions = event='Y',
  model = treatment baseline_BCVA,
  dist = binomial,
  margins = treatment,
  options = cl diff reverse)
```

Chi-Squared test / Fisher's Exact test for comparison between treatments:

```
proc freq data=indata;
  tables outcome*treatment / chisq fisher;
  weight count/zeros;
run;
```

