Robustness analysis for secondary efficacy endpoints will be performed using PP population ODO. In the summaries using PP population ODO, subjects whose dosing regimen was increased from QD to BID starting from Week 4 will be reported separately from the subjects who did not change regimens throughout the study duration under a group called "Netarsudil QD to BID" for the Week 8 visit. The baseline value for these subjects will remain the same. At Week 8 visit, comparisons for efficacy endpoints between subjects treated under QD and subjects who switched from QD to BID will be performed as appropriate. However, a high degree of caution should be exerted when interpreting the results as sample sizes might be smaller.

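### SAP 12.3 has no rule for a responder endpoint with exactly one arm at 0% or 100%: the Wald odds-ratio p-value and CI are then empty, and they are not ranked against the marginal difference

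*SAP*

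**What the plan says.** SAP 2.1 sets the role of the comparison: "The primary comparisons for proportion of subjects achieving a specified endpoint will be between treatment groups". For the 3-line BCVA gain and for complete resolution of corneal edema, at Weeks 4 and 8, SAP 12.3 says the testing "will be completed using logistic regression with fixed effects of treatment and corresponding baseline measure". Protocol 9.8.4 has the same model. The example PROC LOGISTIC code has no FIRTH, EXACT or profile-likelihood option, and its LSMEANS limits are Wald.

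The table is to show "The adjusted odds ratios, marginal proportion of each treatment group, and difference in marginal proportions along with corresponding two-sided 95% CIs and p-values". The odds-ratio p and the marginal-difference p are not ranked. The only stopping rule reads "When none of the subjects in both treatment groups achieve a gain of 3 lines in BCVA, no inferential statistics" and applies to that one endpoint. Pearson's test is also planned, or Fisher's "exact test if any of the cell counts are less than five as a sensitivity analysis". SAP 8.4 adds a display rule: "all odds ratio greater than 999.99 will be presented as" a truncated value, with a matching rule below 0.01.

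Two places allow smaller groups. SAP 12.4 withholds inference on epithelial edema only below five subjects per group. At Week 8 in the per-protocol set, "comparisons for efficacy endpoints between subjects treated under QD and subjects who switched from QD to BID will be performed as appropriate", with no minimum size. Switchers are QD subjects who, in the investigator's opinion, "has not responded adequately to treatment, may have their netarsudil dosing frequency increased to BID for the remainder of the study" (SAP 3.1).

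**The concern.** With about 20 per arm and a demanding responder definition, an arm with no responders is a realistic result. Maximum likelihood then pushes the treatment coefficient towards infinity, and the standard error grows faster than the coefficient. The Wald p drifts to 1 however large the difference between arms. The stopping rule does not reach this case, and the display rule only truncates the printed ratio, leaving its p-value and CI in the table.

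A table could therefore print an odds ratio above 999.99 with p = 0.94 beside a marginal difference with p = 0.003. Both come from the same model and the SAP does not say which to read. The choice would be made after seeing the data.

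**Working it through.** **Inputs.** Up to 20 per arm (SAP 5); two-sided alpha 0.10 (SAP 8.4); model and outputs from SAP 12.3. The documents give no responder rates, so the rates below are assumptions. Unless stated, calculations omit the baseline covariate. SAS was not run; Newton steps stand in for its stopping point.

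**The plan's own figure.** SAP 5 states 80% power for the one-sample t-test on CCT (n = 20, effect size 0.577, alpha 0.10). The noncentral t gives 0.8001, so it reproduces. No power figure is given for any responder endpoint.

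**One separated table, 0/20 v 6/20.**
- Wald odds ratio, z = log OR / SE:
  - 8 steps: 8.36/22.3 = 0.375, p = 0.71
  - 12 steps: 12.36/164.6 = 0.075, p = 0.94 (ratio about 232,000)
  - 15 steps: 15.36/737.7 = 0.021, p = 0.98
  - The 95% CI at 12 steps, 12.36 ± 1.96 × 164.6 on the log scale, would print as below 0.01 to above 999.99.
- Marginal difference: 0.30, SE = √(0.3 × 0.7/20) = 0.1025, z = 2.93, p = 0.003.
- Firth: without a covariate this adds 0.5 to each cell. OR = (6.5 × 20.5)/(0.5 × 14.5) = 18.4, 95% profile CI 1.9 to 2468, penalised likelihood-ratio p = 0.008.
- Fisher: 2 × C(20,6)/C(40,6) = 2 × 38,760/3,838,380 = 0.020.

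With 10 responders in the other arm (and an assumed baseline covariate), the Wald p is still 0.98 at 15 steps, against Fisher 0.0004.

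**How often.** P(exactly one arm empty) = q₁(1 − q₂) + q₂(1 − q₁), with q = (1 − p)²⁰.
- 5% v 20%: 0.3585 × 0.9885 + 0.0115 × 0.6415 = 0.36
- 10% v 30%: 0.1216 × 0.9992 + 0.0008 × 0.8784 = 0.12
- 20% v 40%: 0.01

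**Power at 0.10, exact enumeration of all 21 × 21 tables** (Wald p set to 1 when an arm is at 0% or 100%):

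| Assumed rates | Wald OR | Firth | Marginal difference | Fisher |
|---|---|---|---|---|
| 5% v 20% | 9% | 44% | 44% | 21% |
| 10% v 30% | 32% | 49% | 49% | 34% |
| 20% v 40% | 39% | 41% | 44% | 29% |

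**Type I error at nominal 0.10.**
- 20 per arm, common rates 10% and 20%: marginal difference 0.103 and 0.103; Firth 0.103 and 0.103; Fisher 0.017 and 0.045. In simulations with an assumed baseline BCVA covariate (2,500 trials per setting), the marginal test was 0.12 to 0.14 and Firth 0.08 to 0.09.
- 5 v 5: marginal difference 0.035, 0.097 and 0.178 at rates of 5%, 10% and 20%; Firth 0.044 at 20%. The reason shows in 0/5 v 2/5: z = 0.4/√(0.4 × 0.6/5) = 1.83, p = 0.068, whereas Fisher gives 2 × 10/45 = 0.44.
- 14 QD v 6 switchers (assumed split), rate 20%: marginal difference 0.191, Firth 0.051. For 5/14 v 0/6 the p-values are 0.005 (marginal), 0.116 (Firth) and 0.260 (Fisher).

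**The case against.** The strongest reply is that the plan already holds working tests for this case. A zero cell always triggers Fisher's test, and the marginal difference stays finite. At 20 per arm its power equals Firth's or slightly exceeds it, and without a covariate its size is about nominal. This stands. A reader might infer from the Wald and Firth columns that the plan loses up to 35 points of power (44% − 9%). The documents do not support that, because the marginal difference is planned from the same model. The Wald figure is also low partly by construction.

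A reader might also infer that the marginal test is invalid and should be dropped. At 20 per arm that is not shown. In small groups the inflation depends on the rate: 0.18 at 20% but 0.10 at 10% for 5 v 5. The switcher comparison is a per-protocol robustness analysis, done where appropriate and with a stated caution. Its groups are selected by response rather than randomised, so type I error under equal rates says little there, and Firth does not repair the selection.

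Firth is not the only remedy. Promoting Fisher or using exact logistic regression would also close the gap. But Fisher gives no adjusted odds ratio and is very conservative here.

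What the reply leaves open is the ranking. Fisher is explicitly a sensitivity analysis, and nothing says whether the odds-ratio p or the marginal-difference p is the result.

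**Conclusion.** The defect is real but minor. With exactly one arm at 0% or 100%, the planned Wald odds-ratio p-value and CI carry no information beyond direction. The stopping rule misses the case, and the display rule does not remove those figures. The stronger reading, that the responder endpoints would be left without a usable analysis, does not hold: the marginal difference and Fisher's test remain.

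The consequence is a table that can contradict itself with no stated order. It reaches the four secondary responder endpoints and the exploratory ones; the primary CCT analysis is untouched. SAP 5 says the study is not powered to detect a pre-stated efficacy signal but will inform later designs. How often the case arises rests on assumed rates: 36% of trials at 5% v 20%, and 1% at 20% v 40%. Fewer than 20 evaluable per arm would make it more likely at low rates.

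**What to change.** In SAP 12.3, for all secondary and exploratory responder endpoints:

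1. Fit the odds-ratio model with the FIRTH option. Report profile penalised-likelihood CIs and the penalised likelihood-ratio p-value, named as the main result for the odds ratio. Do not take Wald or LSMEANS limits from the Firth fit: for 0/20 v 6/20 its Wald p is 0.059, against 0.008. At the least, do this whenever an arm is at 0% or 100%, and leave out the ordinary Wald odds-ratio p and CI there.
2. Keep the marginal difference with its CI as a supporting result at about 20 per arm. In the small-group analyses (QD against switchers in 12.3, epithelial edema in 12.4), when an arm is at 0% or 100%, show observed proportions with Firth and Fisher and omit the marginal p-value.
3. Keep Pearson/Fisher as the sensitivity analysis.
4. Extend the both-arms-empty rule to every responder endpoint.
5. Record the departure from Protocol 9.8.4 in SAP 15.

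The cost is a few SAP sentences and some lines of code beyond the FIRTH option, because the planned LSMEANS limits are Wald. The odds ratio shrinks slightly and the test is conservative in very small groups (0.04 at nominal 0.10 for 5 v 5 at a 20% rate). Firth and Fisher can still differ (0/20 v 4/20: 0.043 and 0.106), but their order would be fixed in advance.

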### **7.2 Per Protocol (PP) Population**

The PP population is a subset of the mITT population, which will include those subjects (and their visits) who do not have major protocol deviations likely to seriously affect the primary outcome of the study. This population will be the secondary population for efficacy analyses and will be used to summarize a subset of efficacy variables. If the PP and mITT populations are exactly the same, then additional efficacy analyses on the PP population will not be performed. The PP population will summarize subjects as treated.

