## 12.5 Ad-hoc Efficacy Analyses

If PP population is not exactly the same as mITT population, ad-hoc efficacy tables using mITT population ODO reported as treated may be produced in the same format as efficacy tables using PP population ODO. In the ad-hoc tables, subjects whose dosing regimen was increased from QD to BID starting from Week 4 will be reported under the group “Netarsudil QD to BID” at Week 8 visit. ” If PP population is exactly the same as mITT population, no additional analyses will be performed.

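### The planned Week 8 comparison of QD stayers with QD-to-BID switchers is selected on Week 4 response, but the SAP's caution mentions only small samples

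*SAP*

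**What the plan says.** - **Who is escalated.** SAP 3.1 lets "any subject randomized to netarsudil QD who, in the opinion of the Investigator, has not responded adequately to treatment" go to BID from Week 4. SAP 4.3 says the study is open-label. The switch is permitted, not required.
- **Where switchers appear.** SAP 12.3 makes the PP analysis on observed data a robustness analysis of the secondary endpoints. At Week 8 it reports switchers in a separate QD-to-BID group, keeps their original baseline, and adds that "comparisons for efficacy endpoints between subjects treated under QD and subjects who switched from QD to BID will be performed as appropriate". No test is named.
- **The caution.** It reads: "a high degree of caution should be exerted when interpreting the results as sample sizes might be smaller". Neither 12.3 nor 12.5 mentions how the groups were formed.
- **Optional tables.** SAP 12.5 says that "ad-hoc efficacy tables using mITT population ODO reported as treated may be produced in the same format as efficacy tables using PP population ODO", with the same separate group at Week 8.
- **When these tables exist.** SAP 7.2: "If the PP and mITT populations are exactly the same, then additional efficacy analyses on the PP population will not be performed". Section 12.5 carries the same condition. Section 7.2 also says: "The PP population will summarize subjects as treated".
- **Which comparison leads.** SAP 2.1, for means: "The primary comparisons in this trial will be within a treatment group on the mean change from baseline". For proportions: "The primary comparisons for proportion of subjects achieving a specified endpoint will be between treatment groups".
- **The main Week 8 analysis.** SAP 7.1 and 12.3 place the secondary analyses on mITT, as randomised.

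**The concern.** The stayer and switcher groups are defined by an investigator's reading, at Week 4, of the response that is then compared at Week 8. Small samples widen an interval; selection moves the estimate, and more subjects would not move it back.

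Two further results in the same tables are touched. For mean change the leading comparison is within group, and the Week 8 PP QD column no longer contains the escalated subjects. For proportions the leading comparison is between groups, and section 12.3 does not say which columns enter the PP repeat of QD against BID. If the depleted QD column is set against an intact BID column, the repeat does not test the robustness of the randomised result.

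Protocol 3.2 and SAP 5 say the study is to inform later designs. The stayer–switcher contrast is the only planned efficacy comparison that bears directly on escalation. A reader told only that numbers are small would expect noise around the right answer, when the error has a direction.

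The PP tables concerned are 14.2.1.6, 14.2.2.2, 14.2.3.1.2, 14.2.3.2.2, 14.2.3.3.2 and 14.2.4.2, at Week 8 only.

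**Working it through.** **The plan's own figures (SAP 5).** Power of a one-sample t-test with n = 20, effect size 0.577 and two-sided alpha 0.10 is 80.0% by the noncentral t distribution, as stated. The 90% half-width is given as 60/2.7 = 22.2 µm; the normal formula 1.645 × 60/√20 gives 22.1 and the t formula 23.2. These figures are not in dispute; 22.2 µm serves below as a yardstick.

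**Inputs.** From the plan: SD of change 60 µm, and change calculated as follow-up minus baseline, so negative means thinning. Assumed, because the documents do not give them:
- switch rate p = 0.20, 0.35 or 0.50;
- Week 4–Week 8 correlation r = 0.3, 0.5, 0.7 or 0.9;
- correlation k of the judgement with Week 4 CCT change: 0.5, or 1 as the extreme case;
- escalation benefit b in µm, 0 unless stated.

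**Formulas** (truncated normal; z is the upper p quantile, φ the normal density):
- Stayers minus switchers = -k·r·60·φ(z)/[p(1-p)] + b
- Stayers' mean minus the mean of a QD arm without escalation = -k·r·60·φ(z)/(1-p)
- Switchers' Week 4 to Week 8 change, with no true mean change = -(1-r)·k·60·φ(z)/p - b

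**Worked case,** p = 0.35, r = 0.7, b = 0, φ(z) = 0.3704:
- Stayers minus switchers: k = 1, -0.7 × 60 × 0.3704/0.2275 = -68.4 µm; k = 0.5, -34.2 µm.
- Stayers' column: k = 1, -0.7 × 60 × 0.3704/0.65 = -23.9 µm; k = 0.5, -12.0 µm.
- Switchers' later change: k = 1, -0.3 × 60 × 0.3704/0.35 = -19.0 µm; k = 0.5, -9.5 µm. This is regression to the mean.

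**Ranges over all settings, b = 0 (µm):**

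| Quantity | k = 0.5 | k = 1 |
|---|---|---|
| Stayers minus switchers (truth 0) | -14 to -47 | -29 to -94 |
| Bias of QD column | -3 to -22 | -6 to -43 |
| Switchers' Week 4 to 8 change (truth 0) | -2 to -29 | -5 to -59 |

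If QD and BID are truly equal, the middle row is also the bias of the depleted QD column against BID. It is about 0.1 to 1.0 (k = 0.5) or 0.3 to 1.9 (k = 1) times the 22.2 µm yardstick.

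**With a true benefit of 20 µm,** the contrast should be +20. At k = 1 it is -9 to -74 µm, the wrong sign throughout. At k = 0.5 it is +4 to +6 µm for r = 0.3 and -4 to -27 µm for r = 0.5 to 0.9.

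**QD column against QD as randomised.** The randomised arm includes the switchers, so the difference is p × (stayers minus switchers), and its sign follows that contrast. With k = 0.5, r = 0.3, p = 0.50 and b = 34.6 µm (the plan's example change, borrowed as an upper case), the contrast is -14.4 + 34.6 = +20.2 and the difference is 0.50 × 20.2 = +10.1 µm: the stayers look worse than QD as randomised. With b = 0 it is negative throughout.

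**Selection or sample size?** A separate simulation used 20 QD subjects, mean change -34.6 µm, SD 60 µm and no switching effect. The worst 5 or 10 at Week 4 switched, r was 0.3 to 0.7, and the judgement was exact or had added noise of SD 60 µm. A two-sample t-test at 10% rejected in 17% to 88% of runs. A random split of the same sizes rejected in 10%. The distortion therefore comes from how the groups are formed.

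**The case against.** The strongest reply is that little hangs on these tables. They are supportive, they disappear if PP equals mITT, the as-treated set is optional, and SAP 5 says the study is not powered for a pre-stated signal. The SAP says openly who is escalated and urges strong caution. The words 'as appropriate' commit to no test, so a purely descriptive comparison would satisfy the text. Most inputs above are assumed, and k = 1 equates an investigator's opinion with CCT change alone.

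Much of this stands, and it limits the point. It does not answer it: a comparison is planned, and the reason given for caution is not the main one.

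A reader might also infer more than the documents support:
- *That the QD column has lost all judged non-responders.* Escalation is optional, so some may remain; the column has lost those escalated.
- *That the QD column must look better than QD as randomised.* It may look better or worse, depending on any escalation benefit, as shown above.
- *That an invalid QD-against-BID test is specified.* Section 12.3 is silent on the columns; this is an ambiguity.
- *That an inflated type I error is built in.* The rejection rates apply only if t-tests are used.
- *That section 12.5 itself plans the stayer–switcher comparison.* It only says how switchers are reported; a comparison follows, if at all, from the shared format.
- *That the main results are compromised.* The Week 4 primary analysis precedes escalation, and the mITT Week 8 analyses keep subjects as randomised.

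**Conclusion.** The point holds for the supportive Week 8 PP tables and possibly for the optional as-treated tables. The stayer–switcher contrast does not estimate an effect of dosing frequency. It is biased against escalation whenever the Week 4 judgement is positively related to the Week 8 outcome, which is the only assumption the direction needs. The PP QD within-group mean at Week 8 is likewise biased in favour of QD relative to a QD arm without escalation. A PP repeat of QD against BID is not a valid robustness check if it uses the depleted column.

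The size is illustrative. The k = 0.5 range is the more sober guide; k = 1 is a limit. Only the SD, the arm size and the example mean change come from the plan. The matter should be fixed because the remedy is wording, but it does not threaten the trial's main conclusions.

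**What to change.** 1. In SAP 12.3 and 12.5, present Week 8 stayers and switchers descriptively, without p-values. Label the QD column as not escalated. Replace the caution with: *These groups are defined by escalation following the Investigator's Week 4 assessment of response; differences between them do not estimate an effect of dosing frequency, whatever the sample size.*
2. Base any Week 8 PP test of QD against BID on randomised groups, as a stated exception to the PP as-treated rule, or omit it. State that at Week 8 a comparison of randomised groups estimates QD with optional escalation against BID.
3. If the switchers' change from Week 4 to Week 8 is shown, note that it is subject to regression to the mean.

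**Cost.** SAP text only; conduct, the escalation option and the primary and mITT analyses stay as they are. What is given up: a formal stayer–switcher test, uniform use of the as-treated rule in PP (or the Week 8 PP between-regimen test), and any Week 8 estimate of unescalated QD against BID. The randomised comparison avoids selection but is diluted by QD subjects who took BID after Week 4, so the report should say what it estimates.
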